9.3. Analysis of SF-36, FACIT-F, CLDQ-HCV, and WPAI: Hepatitis C

The transformed scale scores (0 to 100 scale) at Study Baseline, Part 2 Baseline (Week 8), Week 20, End of HCV Treatment (EOT-HCV), FU-12, and EOT-HIV will be presented for each of the 8 domains of the SF-36 (physical functioning, role-physical, bodily pain, general health, vitality, social functioning, role-emotional, and mental health), and for the physical component summary and mental component summary. Following changes will also be presented in similar manner:

- Change from Study Baseline at each visit (if applicable),
- change from Part 2 Baseline at Week 20, EOT-HCV, and FU-12,
- change from EOT-HCV at FU-12.

Scoring of the SF-36 scales will be performed as described in Chapter 6 of the SF-36 Health Survey: Manual and Interpretation Guide, Version 2. A Wilcoxon signed rank test will be used to explore within treatment group changes described above.

The same analyses will be carried out for CLDQ-HCV (overall score), FACIT-F (trial outcome index and total score), and WPAI: Hep C (% overall work impairment due to HCV for subjects who worked in the past week and % activity impairment due to hepatitis C for all subjects), except that, EOT-HIV and change from Study Baseline as EOT-HIV will not be presented.

The calculation algorithms for CLDQ-HCV, FACIT-F, and WPAI:Hep C are described in Appendix 3.

For imputation of missing data in the QOL data, please refer to Section 3.6.1.5.

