	• Grades 1 through 4 adverse events after switching to E/C/F/TAF or F/R/TAF throughout the study and during coadministration with LDV/SOF treatment.
Pharmacokinetics:	Samples collected for potential population PK assessment.
Health Related Questionnaires:	Health related questionnaires will be administered, including the Adherence Visual Analogue Scale (VAS), HIV Treatment Satisfaction (HIVTSQ), Medical Outcome Study Short Form-36 (SF-36), Functional Assessment of Chronic Illness Therapy-Fatigue scale (FACIT-F), chronic liver disease questionnaire (CLDQ-HCV) and work productivity and activity impairment questionnaire (WPAI).
Statistical Methods:	This is a two part, randomized (for HIV therapy) multicenter study to evaluate the efficacy and safety of switching to a F/TAF-based regimen in HCV co-infected subjects on a current suppressive ARV regimen.
	The primary efficacy endpoint is SVR12 (HCV RNA < LLOQ 12 weeks post HCV treatment) in the HCV Full Analysis Set. The primary analysis will use a two-sided exact one-sample binomial test at the 0.05 significance level and construct an associated two-sided exact 95% confidence interval (CI).

Secondary efficacy analyses will evaluate the proportion of subjects with HCV RNA < LLOQ at 4 weeks post coadministration of LDV/SOF treatment. Assessment of HIV-1 RNA \geq 50 copies/mL (virologic failure) will be done at 24 weeks after start of the F/TAF-based regimen using FDA snapshot algorithm. Safety analyses will evaluate adverse events (clinical and laboratory) during switch to F/TAF-based regimen and during coadministration with LDV/SOF treatment. Additional safety analyses will evaluate the proportion of subjects who discontinued from study treatment (HIV or HCV) for an AE.

Additional endpoints to be studied will include the effect of therapy on health-related quality of life.

The assumed SVR12 rate will have at least 85% power to be greater than 8 percentage points from a performance goal of 88% by using a two-sided exact one-sample binomial test at significance level of 0.05.

This study will be conducted in accordance with the guidelines of Good Clinical Practice (GCP) including archiving of essential documents.

GLOSSARY OF ABBREVIATIONS AND DEFINITION OF TERMS

° C	degrees Celsius
° F	degrees Fahrenheit
3TC	lamivudine
AASLD/IDSA	American Association for The Study of Liver Diseases/Infectious Diseases Society of America
ABC	abacavir
AE	adverse event
AIDS	acquired immunodeficiency syndrome

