1.2.2. Randomization and Treatment Groups

Part 1: Approximately 120 subjects will be randomized 1:1 to switch from stable ARV therapy to 1 of the following treatments:

- **Treatment Group 1:** Switch from 2 nucleoside/nucleotide reverse transcriptase inhibitor (NRTI) plus a third ARV agent to E/C/F/TAF fixed dose combination (FDC) (n = 60)
- Treatment Group 2: Switch from 2 NRTI plus a third ARV agent to F/R/TAF FDC (n = 60)

Randomization will be stratified by race (black vs non-black).

Part 2: After 8 weeks on the randomized F/TAF-based regimens, subjects maintaining HIV-1 RNA < 50 copies/mL and tolerating E/C/F/TAF or F/R/TAF through Part 1 will continue the F/TAF-based HIV therapy to which they were randomized and initiate LDV/SOF HCV treatment.

• LDV/SOF FDC tablet once daily for 12 weeks.

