7.1. General Consideration for Safety Analysis

In general, safety data will be summarized for the subjects in the safety analysis set. Safety data collected up to 30 days after permanent discontinuation of all study drugs (including HIV study drug and LDV/SOF) and available data for subject who are still on study drug will be summarized by treatment group and overall, unless specified otherwise. All safety data will be included in listings.

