9. PATIENT REPORTED OUTCOMES

The patient reported outcome (PRO) questionnaires include:

- Visual Analog Scale (VAS) adherence questionnaire for HIV study treatment;
- HIV Treatment Satisfaction Questionnaire (HIV-TSQ) (status form assessed at Study Day 1, and change form at other visits)
- Short Form-36 (SF-36) Version 2 Health Survey.
- FACIT-F
- CLDQ-HCV
- WPAI: Hepatitis C

PRO data will be summarized for the subjects in the safety analysis set. All PRO data collected up to 30 days after subjects who permanently discontinued all study drug will be summarized by treatment group.

Unless otherwise stated, multiple responses and out of range responses will be set to missing and missing responses will not be imputed. The PRO data will be listed.

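### SAP 9.3 tests the quality-of-life questionnaires only within each arm, so it makes no use of the randomised HIV-regimen contrast and splits the common LDV/SOF cohort into two smaller tests

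*SAP*

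**What the plan says.** The design randomises the HIV regimen and then gives one HCV treatment to everyone who continues. SAP 1.2.2: "Approximately 120 subjects will be randomized 1:1 to switch from stable ARV therapy to 1 of the following treatments". In Part 2, subjects in both arms take the same course: "LDV/SOF FDC tablet once daily for 12 weeks".

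The Statistical Methods part of the protocol synopsis gives the aim for the questionnaires: "Additional endpoints to be studied will include the effect of therapy on health-related quality of life". They are completed at Day 1, Weeks 8 and 20, and Post-HCV Treatment Week 12 (Protocol Appendix 2).

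SAP 9 sets the grouping: "All PRO data collected up to 30 days after subjects who permanently discontinued all study drug will be summarized by treatment group". SAP 9.3 lists changes from Study Baseline, "change from Part 2 Baseline at Week 20, EOT-HCV, and FU-12", and change from EOT-HCV at FU-12. Its one test is "A Wilcoxon signed rank test will be used to explore within treatment group changes described above". The other instruments follow SF-36: "The same analyses will be carried out for CLDQ-HCV (overall score), FACIT-F (trial outcome index and total score"), plus two WPAI scores.

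No between-arm or pooled test of these four questionnaires appears in SAP 9, in SAP Appendices 3 and 4, or in Protocol section 8.

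**The concern.** The design supports two questionnaire questions, and a within-arm test of change from zero serves neither well.

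- **HIV regimen.** The comparison protected by randomisation is the difference between arms. The Day 1 to Week 8 change is measured before LDV/SOF starts, so it isolates the HIV switch. The SAP does not estimate this difference. A within-arm change also contains whatever is common to both arms, such as time, regression to the mean, and expectation in an open-label study.
- **LDV/SOF period.** All Part 2 entrants take the same HCV drug, so the change over this period can be estimated in the whole treated cohort. The plan splits it into two tests.

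At stake is how the tables will be read. Two separate p-values per scale invite a comparison of the arms by significance, which they cannot support. The LDV/SOF-period change is also estimated less precisely than the data allow.

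**Working it through.** **The plan's own figure.** The documents give no power, SD or effect size for the questionnaires. The only power statement is for SVR12 (SAP 1.3). With 120 subjects, 96% against 88% and a two-sided 0.05 exact test, rejection occurs at 113 or more successes. Power is 89.1%, so at least 85% is confirmed. It has no bearing on this point.

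**Inputs.** 60 per arm and 120 in all (SAP 1.2.2). Assumed: two-sided 0.05, normal changes, no attrition, the same true change *d* (in SD of change) in both arms, and *d* from 0.1 to 0.5.

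**Formulas.**
- Signed rank power: P(n) = Φ(d·√(n·3/π) − 1.96), where 3/π is the efficiency relative to the paired t test. √(60·3/π) = 7.57 and √(120·3/π) = 10.70.
- Exactly one arm significant: 2·P(60)·(1 − P(60)).

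**Example at d = 0.25.** One arm: Φ(1.89 − 1.96) = 0.473. Pooled: Φ(2.68 − 1.96) = 0.763. Exactly one arm: 2 × 0.473 × 0.527 = 0.499.

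| True change (SD) | Power, one arm (n = 60) | Power, pooled (n = 120) | Exactly one arm p < 0.05 |
|---|---|---|---|
| 0.10 | 11% (simulated) | – | 20% (simulated) |
| 0.20 | 33% | 57% | 44% |
| 0.25 | 47% | 76% | 50% |
| 0.30 | 62% | 90% | 47% |
| 0.40 | 86% | 99% | 25% |
| 0.50 | 97% | >99% | 7% |

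A simulation of 4,000 trials per setting agrees to within one or two points: one-arm power 33%, 48%, 61%, 85% and 96% at 0.2, 0.25, 0.3, 0.4 and 0.5 SD, and exactly one arm significant in 44%, 50%, 48%, 26% and 7%. In the same trials a between-arm rank sum test rejected in 4–6%, close to its nominal level.

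**Change detectable with 80% power**, using 1.96 + 0.84 = 2.80:
- within one arm: 2.80/7.57 = 0.37 SD
- pooled: 2.80/10.70 = 0.26 SD
- between arms: 2.80·√(2/(60·3/π)) = 0.52 SD

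**Number of tests.** SF-36 has 10 scales and 9 changes (5 from Study Baseline, 3 from Part 2 Baseline, 1 from EOT-HCV), giving 90. The five other scores have 8 changes each, giving 40. That is 130 per arm and 260 in all. The tests are correlated, and Week 20 largely coincides with EOT-HCV, but isolated one-arm results are to be expected.

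**The case against.** The case for leaving the plan alone has real substance.

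- **The plan claims little.** SAP 9.3 describes the test as exploratory and says nothing about attributing a change to an HIV regimen. No questionnaire is a primary or secondary endpoint, and Protocol 8.1.4 lists no other endpoints of interest. This stands and limits the severity. It does not make a within-arm p-value informative about the regimens.
- **The questionnaires are not singled out.** A reader might infer that they are the one place where the SAP omits an overall result or a comparison. The documents do not support that. SAP 6.1.2 and 6.1.3 test and estimate SVR12 for each group; bone markers in SAP 7.3.4 are summarised by group only; SAP 5.2 gives no between-group p-value at Part 2 baseline; laboratory data carry no inferential statistics. Elsewhere the practice differs: safety data "will be summarized by treatment group and overall, unless specified otherwise", and arms are compared on the Week 24 HIV outcome (SAP 6.2.2.2) and CD4 change (SAP 6.3.2.7). The SAP is mixed.
- **No data are discarded.** A reader might infer that half the sample goes unused for LDV/SOF. Both arms are tested and reported; the loss is of precision in each test.
- **Pooling does not establish cause.** A pooled before-after test has the same common influences as a within-arm one, and no group goes without LDV/SOF. It gains precision, not attribution.
- **The between-arm contrast has limits.** The study is open-label and the outcomes are self-reported. SAP 3.2 groups these data by treatment received, though this differs from assignment only when it does so for the whole treatment duration. Only differences of about 0.5 SD are detectable with 80% power. An interval showing that uncertainty is still more useful than two separate p-values.

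**Conclusion.** The point holds as a minor one. The exploratory analysis of these four questionnaires makes no use of the randomised comparison between HIV regimens, and it splits a cohort with a common LDV/SOF course into two tests of at most about 60 subjects each.

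Under the stated assumptions, significance in exactly one arm occurs in about 44–50% of trials at a common change of 0.2–0.3 SD. It is much rarer at the ends of the range (20% at 0.1 SD, 7% at 0.5 SD). A one-arm-only result is therefore not evidence of a regimen difference. Pooling raises power from about 33% to 57% at 0.2 SD, 48% to 76% at 0.25 SD and 61% to 90% at 0.3 SD.

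The effect sizes are assumptions. The power figures are upper bounds: some subjects will not enter Part 2, missing forms are not imputed (SAP 3.6.1.5), and the WPAI work score covers only those who worked. No primary or secondary conclusion depends on this.

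**What to change.** Amend SAP 9 and 9.3 as follows.

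1. Present the questionnaires by treatment group and overall. Run the signed rank tests of change from Part 2 Baseline and from EOT-HCV on all LDV/SOF-treated subjects combined. State that this is an uncontrolled before-after change that cannot by itself be attributed to LDV/SOF.
2. For change from Study Baseline, add a between-arm difference with 95% CI: Hodges-Lehmann with the rank sum test, or ANCOVA on the baseline score. Name Day 1 to Week 8 as the main HIV-regimen contrast. Note that the study is open-label, that later visits are conditional on entering Part 2, and that only differences of about 0.5 SD are detectable with 80% power.
3. Keep within-arm changes as descriptive statistics.

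The cost is SAP wording, an overall column and a few lines of programming, with no new data, visits or subjects. The per-arm p-values are given up.

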11. SOFTWARE

SAS® Software Version 9.4. SAS Institute Inc., Cary, NC, USA.

nQuery Advisor(R) Version 7.0. Statistical Solutions, Cork, Ireland.

12. SAP REVISION

Revision Date (DD MMM YYYY)	Section	Summary of Revision	Reason for Revision

13. APPENDICES

Appendix 1. Study Procedure Table

Appendix 2. Flowchart of US FDA-Defined Snapshot Algorithm (for Switch Study Trial)

Appendix 3. QOL Score Calculation Algorithms
Appendix 4. Programming Specification

Appendix 1. Study Procedure Table

			End of Week ^c			End of Week ^c – Part 2						
				rt 1 eatment	O	n Tre	eatme	nt	Post-HCV	Treatment	30-Day	
	Screeninga	Day 1 ^b	4	6	8	12	16	20	4	12	Follow-Up ^d	ESDD ^e
Written Informed Consent	X											
Medical History	X											
Liver Cirrhosis Determination	X											
Concomitant Medications	X	X	X		X	X	X	X	X	X	X	X
Adverse Events	X	X	X		X	X	X	X	X	X	X	X
Complete Physical Examination	X	X								X		X
Symptom-Directed Physical Examination f			X		X	X	X	X	X		X	
Vital Signs & Weight	X	X	X		X	X	X	X	X	X	X	X
Height	X											
12-Lead ECG (performed supine)	X											X
Urinalysis & Urine Chemistry	X	X	X		X	X	X	X	X	X	X	X
Urine Storage Sample		X	X		X	X	X	X	X	X		X
Urine Pregnancy Test ^g		X	X		X	X	X	X	X	X	X	X
Serum Pregnancy Test ^g	X											
Chemistry Profile ^h	X	X	X		X	X	X	X	X	X	X	X
Hematology Profile ⁱ	X	X	X		X	X	X	X	X	X	X	X
Coagulation Assessments ^j	X	X	X		X	X	X	X	X	X		
Metabolic Assessments ^k		X			X			X		X		
CD4+ Cell Count	X	X	X		X	X	X	X	X	X	X	X
Plasma HIV-1 RNA	X	X	X	X	X	X	X	X	X	X	X	X
HIV-1 Proviral Genotype ^l	X											
HIV-1 Genotype/Phenotype ^m												X

			End of Week ^c Part 1 On Treatment		End of Week ^c – Part 2							
					On Treatment			nt	Post-HCV Treatment		30-Day	
	Screeninga	Day 1 ^b	4	6	8	12	16	20	4	12	Follow-Upd	ESDD ^e
Plasma HCV RNA	X	X			Х	X	X	X	X	X	X	X
HCV Genotype & Subtype	X											
HCV IL28B Genotype	X											
HIV, HBV & HCV Serologies ⁿ	X											
Evaluations of Bone & Renal Safety, Inflammation and Platelet and Coagulation Function ^o		Х	Х		X	Х		Х		X		Х
Plasma Storage Sample ^p		X	Х	X	Х	Х	Х	Х	X	X		X
Serum Storage Sample ^p	9	X	X		Х	Х	Х	Х	Х	X		Х
PPD		Х	Х		Х			Х		X		Х
Estimated GFR _{CG} ^r	X	Х	Х		Х	Х	Х	Х	X	X		Х
Population PK ^s	2.0		X		Х	Х	Х	Х				
Health Related Questionnaires ^t		X			X			Х		X		Х
Randomization	1	X										
Study Drug Dispensation and Accountability ^u		Х	Х	ģ	Х	X	X	Х	Х	X		$X^{\mathbf{v}}$

[figure not shown]
- a Evaluations to be completed within 42 days prior to the Day 1 visit
- b Subjects will be dispensed HIV study drugs only at the Day 1 visit; initiation of HIV treatment with the study drugs must take place within 24 hours after the Day 1 visit.
- c All study visits are to be scheduled relative to the Day 1 visit date. Visit windows are ± 2 days of the protocol specified date through Post-HCV Treatment Week 4 visit, and ± 4 days of the protocol specified date at Post-HCV Treatment Week 12.
- d For the purpose of scheduling a 30-Day Follow-Up Visit, $a \pm 6$ days window may be used
- Early Study Drug Discontinuation visit to occur within 72 hours of last dose of study drug. Refer to Section 6.5.1 of the protocol for management of early study drug discontinuation of Parts 1 and 2.
- f Symptom-directed physical examination as needed
- g For females of childbearing potential only as defined by Appendix 5 of the protocol. Positive urine pregnancy tests will be confirmed with a serum test.
- h Chemistry profile: alkaline phosphatase, AST, ALT, total bilirubin, direct and indirect bilirubin, total protein, albumin, bicarbonate, BUN, calcium, chloride, creatinine, glucose, phosphorus, magnesium, potassium, sodium, and uric acid. At visits in which metabolic assessments are to be performed, analyses of glucose will be done as part of the fasting metabolic assessments and not as part of the chemistry profile
- i CBC with differential and platelet count

- j Coagulation assessments: International Normalized Ratio (INR), prothrombin time (PT), and activated partial thromboplastin time (APTT)
- k Metabolic assessments (collected fasted, no food or drink, except water, at least 8 hours prior to blood collection): glucose and lipid panel (total cholesterol, HDL, direct LDL, and triglycerides)
- 1 If a historical genotype report prior to first ARV is not available, or subject has 3 or more prior ARV regimens, whole blood sample for proviral genotype analysis of archived resistance
- m HIV-1 genotype/phenotype resistance testing for subjects with unconfirmed virologic rebound with HIV-1 RNA value ≥ 400 copies/mL
- n Serology testing includes HIV and HCV antibody, and HBV core antibody (HBcAb), surface antibody (HBsAb), surface antigen (HBsAg), e-antibody (HBeAg), e-antibody (HBeAb), and HBV DNA.
- o Blood for bone safety, parathyroid (PTH) and serum OH-25 vitamin D; Inflammation may include cystatin-C, IL-6, hs-CRP, sCD14, sCD163, sTNF-1R, and Lp-PLA2; Platelet and coagulation function may include soluble glycoprotein VI (sGPVI), P-selectin, soluble CD40 ligand, and D-dimer will be collected. Urine for renal safety, including retinol binding protein, beta-2-microglobulin, urine albumin, and urine protein will be collected. Samples will be collected fasted. If the subject has not fasted prior to the visit, the visit may proceed, but the subject must return within 72 hours in a fasted state.
- p Plasma storage samples for safety, virology, and/or PK testing. Serum storage samples for possible additional clinical testing.
- a PPD
- r Estimated GFR according to the Cockcroft-Gault formula for creatinine clearance (see Section 4.2 of the protocol for details)
- s Two (2) blood samples will be collected: 1) the predose sample should be drawn prior to observed study drug dosing; 2) the postdose sample should be drawn between 15 mins and 4 hours postdose
- t Health related questionnaires: adherence for HIV (VAS), HIV-TSQs Status version (at Day 1 only), HIV-TSQc Change version (at all other visits), SF-36, FACIT-F, CLDQ-HCV, and WPAI: Hepatitis C.
- Part 1: HIV study drugs are dispensed after all Day 1 assessments are completed and randomization occurred, and through the duration of the study.

 Part 2: After determination of HIV suppression (< 50 copies/mL) based on the Week 6 HIV-1 RNA value and tolerability of HIV study drugs, LDV/SOF will be dispensed at Weeks 8, 12, and 16 only.
 - Post-HCV Treatment Week 12: drug accountability only; study drug will not be dispensed at this visit.
- v If subjects discontinue during Part 1, only drug accountability will be performed; study drug will not be dispensed at this visit. In Part 2, if subject discontinues LDV/SOF but still continues with HIV study drug, HIV study drug will be dispensed until the last study visit. If subject discontinues HIV study drug but still continues with LDV/SOF, LDV/SOF will be dispensed. If subject discontinues both HIV and HCV study drugs, only drug accountability will be performed; no dispensation will occur at this visit.

Appendix 2. Flowchart of US FDA-Defined Snapshot Algorithm (for Switch Study Trial)

The following flowchart for US FDA-defined snapshot algorithm is based on the US FDA Guidance on Human Immunodeficiency Virus-1 Infection: Developing Antiretroviral Drugs for treatment {U. S. Department of Health and Human Services 2015}

^{*} On-Treatment HIV-1 RNA data include all HIV-1 RNA data for subjects who are on-going and HIV-1 RNA data up to 1 day after the last dose date of study drug for subjects who prematurely discontinue or complete study drug.

Appendix 3. QOL Score Calculation Algorithms CLDQ – HCV

CLDQ-HCV scores are calculated using subject responses to 29 questions in the questionnaire. If Ri is the score for the patient's response to the item i, for i=1, 2,, 29 then the 4 domain scores are calculated as follows:

- Activity/Energy (AE) = Mean of {R1, R3, R4, R5, R7, R18}
- Emotion (EM) = Mean of {R6, R8, R9, R11, R16, R23, R24, R27, R28}
- Worry (WO) = Mean of {R14, R15, R17, R19, R20, R21, R22, R29}
- Systemic (SY) = Mean of {R2, R10, R12, R13, R25, R26}

Here "Mean" is the average of nonmissing items (SAS mean function). Each score is calculated only if at least half of corresponding items are not missing. Otherwise, the score will be missing.

Over all CLDQ-HCV score is calculated by taking the mean of 4 domain scores {AE, EM, WO, SY}.

FACIT-F

Patient responses to 40 questions in FACIT-F questionnaire are rated in 0-4 score.

If less than 50% of responses in the corresponding domain are missing, the subscales for five domains are calculated as follows:

- Physical Well-Being (PWB) = $7 \times \text{Mean of } \{\text{GP1-GP7}\}\$
- Social/Family Well-Being (SWB) = $7 \times$ Mean of {GS1-GS7}
- Emotional Well-Being (EWB) = $6 \times \text{Mean of } \{\text{GE1-GE6}\}$
- Functional Well-Being (FWB) = $7 \times \text{Mean of } \{GF1\text{-}GF7\}$
- Fatigue Subscale (FS) = 13 × Mean of {HI7, HI12, An1-An5, An7, An8 An12, An14-An16} and
- FACIT-F Trial Outcome Index (TOI) = PWB+FWB+FS

If less than 20% of all 40 questions are not missing,

• TACIT-F Total Score = PWB+SWB+EWB+FWB+FS

WAPI: Hepatitis C

The response to Question 1 of this questionnaire provides the binary endpoint whether or not the subject had been in a paid employment during the week prior to assessment.

If the subject had been in a paid employment (Response to Q1 is "Yes") at the visit when questionnaire was given, then following three scores are derived:

- Percent work time missed due to hepatitis $C = 100 \times Q2 / (Q2 + Q4)$
- Percent impairment while working due to hepatitis $C = 100 \times Q5 / 10$
- Percent overall work impairment due to hepatitis C =

$$100 \times \left[\frac{Q2}{(Q2+Q4)} + \left(1 - \frac{Q2}{Q2+Q4)} \right) \times \frac{Q5}{10} \right]$$

Question 6 is applicable to all subjects:

• Percent activity impairment due to hepatitis $C = 100 \times Q6 / 10$.

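### As written, the SAP's FACIT-F total-score rule conflicts with its subscale rule, so no subject could ever receive a total score

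*SAP*

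**What the plan says.** The FACIT-F algorithm is in SAP Appendix 3. It sets the instrument's size: "Patient responses to 40 questions in FACIT-F questionnaire are rated in 0-4 score". The subscales come first, under this condition: "If less than 50% of responses in the corresponding domain are missing, the subscales for five domains are calculated as follows". Each subscale is the mean of the domain's items multiplied by the number of items, for example "Fatigue Subscale (FS) = 13 × Mean of {HI7, HI12, An1-An5, An7, An8 An12, An14-An16". The Trial Outcome Index follows: "FACIT-F Trial Outcome Index (TOI) = PWB+FWB+FS".

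A separate condition then introduces the total: "If less than 20% of all 40 questions are not missing". The formula beneath it is "TACIT-F Total Score = PWB+SWB+EWB+FWB+FS" (the instrument's name is misprinted).

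Section 9.3 makes this score an analysis variable. It lists "FACIT-F (trial outcome index and total score" among the measures to be handled in the same way as SF-36, and sends the reader to Appendix 3 for the calculation. Section 9 states that, unless the plan says otherwise, "missing responses will not be imputed".

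**The concern.** An item that is not missing is an answered item, so the condition grants a total score only to nearly blank questionnaires. The total is also a plain sum of five subscales, and those exist only when each domain is more than half answered. The two requirements pull in opposite directions.

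Section 9.3 plans FACIT-F total-score summaries at Study Baseline, Part 2 Baseline, Week 20, end of HCV treatment and FU-12. It also plans changes from Study Baseline, from Part 2 Baseline and from end of HCV treatment, with within-group Wilcoxon signed rank tests. If the rule is coded as it stands, all of these outputs are empty. If a programmer silently repairs it, the reported score rests on a rule that the plan does not contain.

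**Working it through.** **Inputs (all from SAP Appendix 3).** The item lists give five domains. The fatigue list counts as HI7 and HI12 (2), An1 to An5 (5), An7, An8 and An12 (3), and An14 to An16 (3), which makes 13.

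| Domain | Items n | Fewest answered a with (n − a)/n < 0.5 |
|---|---|---|
| Physical (PWB) | 7 | 4 |
| Social/family (SWB) | 7 | 4 |
| Emotional (EWB) | 6 | 4 |
| Functional (FWB) | 7 | 4 |
| Fatigue (FS) | 13 | 7 |
| Total | 40 | 23 |

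**Reproducing the plan's figure.** 7 + 7 + 6 + 7 + 13 = 40, which matches the stated number of questions.

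**Subscale rule.** All five subscales need at least 4 + 4 + 4 + 4 + 7 = 23 answered items (23/40 = 57.5%). Reading the rule as at most 50% missing lowers only the emotional domain, from 4 to 3, and the sum to 22.

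**Total-score rule as written.** Answered/40 < 0.20 means fewer than 8 answered, so at most 7 (7/40 = 17.5%; 8/40 is already 20%).

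**The two together.** At most 7 answered and at least 23 answered (or 22 on the looser reading) cannot both hold. With 7 answered items at most one subscale exists, because any two need at least 4 + 4 = 8.

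**Enumeration.** The possible counts of answered items per domain give 8 × 8 × 7 × 8 × 14 = 50,176 patterns. Of these, 1,344 have all five subscales and 791 meet the total-score condition as written. None does both.

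**With the negation removed.** Missing/40 < 0.20 means at most 7 missing, so at least 33 answered (82.5%). This too is met by 791 patterns. In 500 of them all five subscales exist. In the other 291 at least one subscale is still unavailable. For example, 3 of the 6 emotional items missing and everything else answered leaves only 3/40 = 7.5% missing overall, yet that domain is exactly half missing and gets no score. These are counts of patterns, not probabilities. They show that the corrected rule works and that the subscale condition still matters alongside it.

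**The case against.** The best reply is that this is a slip of the pen. The same appendix misprints the names of two instruments. The subscale rule a few lines above is phrased in terms of items missing, and deleting one word makes the two rules compatible, so the intent can be recovered. Literal coding would produce an empty total-score table beside a populated Trial Outcome Index, and the fault would show on the first run. It could not bias a result unnoticed, and the item responses would remain in the database. The rule also lacks the explicit exclusivity of the CLDQ-HCV rule in the same appendix, which says what happens when its condition fails. Finally, FACIT-F is neither a primary nor a secondary endpoint, and the signed rank tests are exploratory.

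Most of this stands, and it limits the importance of the point. It does not make the rule usable. If the condition is not exclusive, the plan simply has no rule for a completed questionnaire. Nothing elsewhere fills the gap: the SAP revision table has no entries, the reference list contains no FACIT scoring source, and no rule allows summing only the available subscales. For SF-36, by contrast, Section 9.3 names a scoring manual. The repair also involves a choice of boundary: deleting the negation requires at least 33 answered items, whereas a rule of at least 80% answered would require 32.

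**Conclusion.** The point holds. As specified, the FACIT-F total score cannot be calculated for any subject: at most 7 answered items are permitted where at least 23 are needed. This rests on the literal wording, on the item lists printed in Appendix 3, and on the total being a plain sum that needs all five subscales. It describes what literal coding would produce and does not predict that the sponsor would report an empty table.

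The scope is narrow. One planned patient-reported score is affected. The Trial Outcome Index is defined before the faulty line and does not depend on it. SF-36, CLDQ-HCV, WPAI, SVR12, SVR4 and the HIV endpoints are unaffected. The line should be corrected because it is the operative definition of an analysis variable, but it does not threaten the trial's main conclusions.

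**What to change.** In SAP Appendix 3, replace the condition so that the FACIT-F total is calculated when fewer than 20% of the 40 items are missing (at least 33 answered) and all five subscales are calculable, and is otherwise set to missing. Correct the misprinted instrument name on the same line. The sponsor should confirm the threshold, including whether 32 answered items suffice, against the scoring source it intends to follow, and cite that source.

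The cost is one line of the appendix and an entry in the revision table, made before the analysis is run. Data collection, sample size and the other analyses do not change.
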